10.8.4 Missing Data

All attempts will be made to avoid missing data. However, missing values will remain as missing, i.e., no attempt will be made to impute. In general, only observed values will be used in data analyses and presentations. The one exception to this is summarizing concentration data; values that are detectable but below the lower limit of quantification (LLOQ) will be set to one-half the value LLOQ; concentrations below the limit of detection will be set to 0. Otherwise, no imputation is anticipated. No transformation will be applied.

11 DATA HANDLING AND RECORDKEEPING

11.1 Data Management Responsibilities

Data collection tools will be developed by the CDM(s) in conjunction with the protocol team. Quality control and data integrity are managed manually and systematically with reports and queries routinely generated and provided by the CDM(s) to the study sites for verification and resolution. As part of the study activation process, each study site will identify all CRFs to be used as source documents. Study CRF data will be entered and cleaned using a data management system compliant with the ICH Good Clinical Practices (GCP) and US CFR guidelines for electronic data capture.

IDI files generated in the field will be electronically transferred to RTI International using a secure File Transfer Protocol (FTP) site, where they will be uploaded and managed using a qualitative software package. RTI International will act as a hub and manage all qualitative data for the study. A convention for file naming will be developed, and all data will be labeled according to this process. Transcripts will be transferred to RTI International as they are completed. RTI International will save all versions of all files on a secure, password-protected server in the US.

11.2 Source Documents and Access to Source Data/Documents

All study sites will maintain source data/documents in accordance with MATRIX's Good Documentation Practice (GDP) guidelines (www.matrix4prevention.org).

Each IoR/designee will maintain, and store securely, complete, accurate and current study records throughout the study. In accordance with U.S. regulations, for the investigational products tested, IoRs/designees will maintain all study documentation for at least two years following the date of marketing approval for the indication in which they were studied. If no marketing application is filed, or if the application is not approved, the records will be retained for two years after the investigation is discontinued, or longer as per local regulatory requirements and the US FDA is notified.

Study records must be maintained on site for the entire period of study implementation. Thereafter, instructions for record storage will be provided by CONRAD. No study records may be moved to an off-site location or destroyed prior to receiving approval from CONRAD.

11.3 Quality Control and Quality Assurance

Study sites will conduct quality control and quality assurance procedures in accordance with MATRIX's Quality Management Plan (www.matrix4prevention.org).

12 CLINICAL SITE MONITORING

Study monitoring will be carried out by ACRO for the African sites and by CRA Resources for the US site. Study monitors will do the following:

- Review informed consent forms, procedures, and documentation
- Assess compliance with the study protocol, ICH GCP guidelines, and applicable regulatory requirements (US and non-US), including US Code of Federal Regulations (CFR) Title 45 Part 46 and Title 2 Parts 200 and 225
- Perform source document verification to ensure the accuracy and completeness of study data
- Verify proper collection and storage of biological specimens
- Verify proper storage, dispensing, and accountability of investigational study products
- Assess implementation and documentation of internal site quality management procedures

Monitoring visits may be conducted on-site or remotely. Remote visits may include remote source document verification using methods specified for this purpose. Remote monitoring visits may be performed in place of or in addition to onsite visits to ensure the safety of study participants and data integrity.

For on-site visits, the IoR/designee will allow study monitors to inspect study facilities and documentation (e.g., informed consent forms, clinic and laboratory records, other source documents, CRFs), as well as observe the performance of study procedures. The IoR/designee also will allow inspection of all study-related documentation by authorized representatives of MATRIX, CONRAD, USAID, FDA, SAHPRA, KPPB, OHRP, IRBs/IECs and other local, US, or international regulatory authorities. A site visit log will be maintained at the study site to document all visits.

13 HUMAN SUBJECTS PROTECTIONS

Site investigators will make efforts to minimize risks to participants. Participants and study staff members will take part in a thorough informed consent process. Before beginning the study, IoRs/designees will have obtained IRB/IEC approval and the protocol will have been submitted to the FDA and other applicable national drug regulatory authorities. IoRs/designees will permit audits by USAID, the FDA, SAHPRA, KPPB, OHRP, MATRIX, IRBs/IECs, and other local, US, or international regulatory authorities or any of their appointed agents.

Changes to this protocol may be implemented by investigators prior to IRB/IEC approval, if those changes are required to eliminate apparent immediate hazards to the study participant; see 45

CFR 46.108(a)(3)(iii) under the 2018 Requirements (<https://www.ecfr.gov>). These changes must be documented as Protocol Deviations and reported to the Protocol Team and IRBs/IECs as soon as possible; see ICH E6(R2), Good Clinical Practice, Section 4.5.4 (<https://www.fda.gov/science-research/clinical-trials-and-human-subject-protection/ich-guidance-documents>). In the event of a public health emergency, investigators should adhere to the recommendations of their local institutions, IRBs/IECs and local health departments. When conflicts exist between local directives, MATRIX, Protocol Team and/or USAID policies or guidance, sites should follow the requirement that is most protective of study participants and site staff.

13.1 Institutional Review Boards/Ethics Committees

The participating institution is responsible for assuring that this protocol, the associated site-specific informed consent forms (ICFs), and study-related documents (such as participant education and recruitment materials) are reviewed by an IRB/IEC responsible for oversight of research conducted at each study site and, as required, by applicable national DRA. Any amendments to the protocol must be approved by the responsible IRBs/IECs and (if applicable) national DRA prior to implementation.

Subsequent to the initial review and approval, the responsible IRBs/IECs must review the study at least annually. Each IoR/designee will make safety and progress reports to the IRBs/IECs at least annually and within three months after study termination or completion. These reports will include the total number of participants enrolled in the study, the number of participants who completed the study, all changes in the research activity, and all unanticipated problems involving risks to human subjects or others. In addition, the results of all ISP reviews of the study will be provided to the IRBs/IECs.

13.2 Protocol Implementation

Prior to implementation of this protocol, and any subsequent full version amendments, each site must have the protocol and the protocol consent forms approved, as appropriate, by their local IRBs/IECs and any other applicable regulatory entities. Upon receiving final approval, sites will submit copies of all relevant protocol/amendment documents (i.e., IRB/IEC approval letters with a detailed list of approved documents, approved ICF documents, etc.) to the MATRIX Clinical Trials Hub Regulatory team.

The MATRIX CRM(s) will review the submitted document packet to ensure receipt of all required protocol/amendment documents prior to study activation at the sites. Sites will receive a Study Activation Notification from the MATRIX CRM(s) that indicates successful completion of the protocol readiness process. A copy of the Study Activation Notification should be retained in the site's regulatory files.

Upon receiving final IRB/IEC and any other applicable approval(s) for a protocol/amendment, sites are required to submit copies of all relevant protocol/amendment documents (i.e., IRB/IEC submission letters, IRB/IEC approval letters with a detailed list of approved documents, related correspondence with IRB/IEC, approved ICF documents, etc.) to CONRAD prior to study activation. Upon receiving final IRB/IEC and any other applicable approval(s) for an amendment, activated sites should implement the amendment immediately but are still required to submit copies of all relevant amendment documents to CONRAD.

13.3 Study Coordination

CONRAD holds the Investigational New Drug (IND) application for this study. Delegation of any sponsor responsibilities for this study will be specified in writing between CONRAD and MATRIX

Study implementation will be directed by this protocol, which may not be amended without prior written approval from the Protocol Co-Chairs and Protocol Team representatives from MATRIX and USAID. Study implementation will also be guided by a common SSP Manual that provides further instructions and operational guidance on conducting study visits; data and forms processing; specimen collection, processing, and shipping; AE assessment, management and reporting; dispensing study products and documenting product accountability; and other study operations. Standardized study-specific training will be provided to sites by the MATRIX CRM(s) and other designated members of the Protocol Team.

Close coordination between protocol team members is necessary to track study progress, respond to queries about proper study implementation, and address other issues in a timely manner. The PSRT will address issues related to study eligibility and AE management and reporting as needed to assure consistent case management, documentation, and information-sharing across sites. Rates of accrual, adherence, follow-up, and AE incidence will be monitored closely by the team as well as the ISP and the MATRIX Clinical Trials Hub.

13.4 Risk Benefit Statement

13.4.1 Risks

General

The study may cause an inconvenience to daily life due to visit scheduling. Participants will need to refrain from vaginal and anal activity, including sex, during study participation at specified timepoints.

Phlebotomy

Phlebotomy may lead to discomfort, feelings of dizziness or faintness, and/or bruising, swelling, having a blood clot, excessive bleeding, and/or infection.

Pelvic Examination and Procedures

The pelvic examination with speculum insertion may cause discomfort, redness, itching, and/or irritation in the external genital and vaginal area.

CVF/CVL Collection

Collection of CVF may cause discomfort or pressure in the vagina or genital area.

RF Collection

There is the risk of mild discomfort in addition to a slight risk of bleeding with the insertion of rectal swabs and sponges for collection of RF.

CVT Biopsy Collection

There is a risk of mild pain and/or sharp pinch when biopsies are taken. Bleeding sometimes occurs after biopsy collection and can usually be stopped with pressure or medication to the biopsy area. If medicine is used, it may cause temporary dark-colored discharge from the vagina. In rare cases, a stitch might need to be placed to stop the bleeding. Soreness and discomfort in the vagina may occur for one to two days after the procedure along with some vaginal spotting. There is a small risk of infection and heavier bleeding. Participants will be instructed to contact the clinic if symptoms are bothersome, if heavy bleeding is noted or if the participant develops any abnormal odor or discharge from the vagina. Participants will be counselled to refrain from NSAIDs or aspirin use 3 days before and after PK sample collection.

Other Risks

Disclosure of HIV and STI status may cause worry, sadness or depression. Disclosure of HIV-positive status has been associated with depression, suicidal ideation, and denial as well as social isolation. Trained study staff will be available to help participants deal with these feelings.

Participation in clinical research includes the risks of loss of confidentiality and discomfort with the personal nature of questions when discussing sexual behaviors.

Sexual partner notification in response to diagnosed STI or HIV infection could cause problems in participants' relationships. Participants also could have problems in their partner relationships associated with study-required abstinence.

Site staff will make every effort to protect participant privacy while in the study. Although study sites will make every effort to protect participant privacy and confidentiality, it is possible that participants' involvement in the study could become known to others, and that social harms may result (i.e., because participants could become known as HIV-positive or at "high risk" for HIV infection). For example, participants could be treated unfairly or discriminated against, or could have problems being accepted by their families and/or communities.

Risks Associated with vaginal inserts

The inserts may cause irritation of the vagina and external genitalia, including pain, itching, irritation, vaginal discharge, or rash. The insert may also cause urinary symptoms including dysuria, frequency, or urgency.

Risks Associated with oral TAF and oral EVG

There is a low probability of adverse events associated with systemic levels of TAF and EVG. Those include: headache, nausea, fatigue, diarrhea, abdominal pain, back pain, cough, arthralgia, and dyspepsia. These side effects may or may not be associated with the use of TAF or EVG when the drugs are administered vaginally.

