6.7.2 Prohibited Practices

Participants will be asked to abstain from any vaginal and anal activity, douching, and use of all intravaginal objects and products at the times specified below.

- Beginning 48 hours before enrollment visit, during daily dosing phase and approximately 48 hours before and 10 days after CVT biopsy collections:
 - Vaginal and/or anal intercourse
 - Finger stimulation
 - Insertion of fingers or any objects into the vagina or rectum including
 - Sex toys, female condoms, diaphragms, or other vaginal barrier methods
 - Menstrual cups and tampons (acceptable to use outside of dosing phases)
- 72 hours before and after CVT biopsy collections:
 - Use of aspirin greater than 81 mg
- For the duration of the study:
 - Use of any drugs which could prolong bleeding and/or clotting or otherwise interfere with study results per study criteria (i.e., daily NSAID use, St. John's Wort, blood thinners, etc.)
 - Use of vaginal products including spermicides, lubricants, douches, medications, moisturizers, or contraceptive vaginal rings

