7.2 Baseline Visits

7.2.1 Enrollment Visit – Visit 2

The enrollment visit should be scheduled within 8 weeks of Screening/Visit 1. Willing and eligible participants will be asked to complete a baseline acceptability questionnaire, provide a urine sample for a UPT and undergo HIV screening, provide a blood sample for plasma archive, and undergo baseline sample collection of CVF for PD, CVT for subclinical safety and PD, and cervicovaginal lavage (CVL) collection. Willing and eligible participants will be scheduled after menstrual flow ceases and ideally in the luteal phase of the menstrual cycle.

Table 2: Enrollment Visit

Enrollment Visit – Visit 2		
Component		Procedures
Administrative and Regulatory		
 ● Confirm participation ● Confirm eligibility ● Review/update locator information ● Provide reimbursement ● Schedule next visit/contact, if indicated
Behavioral/Counseling		
 ● Naïve product use assessment ● Baseline behavioral questionnaire ● Protocol requirements/prohibited vaginal and anal activity ● Pre- and post-test HIV counseling, and risk reduction counselling
Clinical		
 ● Review/update medical and menstrual history ● Assess CM ● Pelvic exam ● Directed physical examination, if indicated ● Vital signs and weight ● Treat or prescribe treatment for RTI/UTI/STIs, if indicated ● Provide available test results
Laboratory	Urine	
 ○ Pregnancy test ○ Urine dipstick/urinalysis, if indicated
	Blood	
 ○ HIV ○ Plasma archive
	Genital	
 ○ PSA test for semen ○ Gram stain for Nugent score, pH ○ CVF for anti-HIV and anti-HSV ○ CVL for soluble markers ○ Vaginal biopsy (BXV) for immunohistochemistry (IHC) ○ Ectocervical biopsy (BXC) for HIV (EVMS only) ○ TV, GC, CT testing, if indicated ○ Saline/KOH wet mount for candidiasis and/or BV, if indicated

7.2.2 Randomization Visit – Visit 3

Visit 3 should be scheduled 10-14 days after Visit 2, not less than 10 days after biopsy. Visit 3 will be scheduled shortly after menstrual flow ceases for cycling participants to ensure the 3 days of product use do not occur during a menstrual cycle.

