Participants will provide a urine sample for a UPT and undergo HIV screening prior to randomization. Participants will also complete a brief product use assessment and undergo baseline pre-insertion sample collection of CVL, CVF for PK, PD, and vaginal microbiota, and (if participant agrees) RF for PK. Provided they have negative HIV and pregnancy test results, participants will be randomized (1:1) to receive TAF/EVG versus placebo vaginal insert. Participants will also be randomized (1:1:1) into three time points for PK tissue sampling after the last dose (24, 48, or 72 hours post last dose).

Participants will then self-administer the first dose (single combination insert of TAF/EVG or placebo) in the clinic. Participant will be dispensed doses 2 and 3 for daily insertion at home.

Table 3: Randomization Visit

Randomization Visit – Visit 3		
Component		Procedures
Administrative and Regulatory		
 ● Confirm participation ● Conduct product assignment randomization (after HIV and pregnancy tests) ● Conduct PK tissue sampling randomization (after HIV and pregnancy tests) ● Review/update locator information ● Provide reimbursement ● Schedule next visit/contact
Behavioral/Counseling		
 ● Protocol requirements/prohibited vaginal and anal activity ● Pre- and post-test HIV counseling, and risk reduction counselling ● Initial product use assessment
Clinical		
 ● Review/update medical and menstrual history ● Assess adverse events (AE) and CM ● Pelvic exam pre-dosing ● Directed physical examination, if indicated ● Vital signs and weight ● Treat or prescribe treatment for RTI/UTI/STIs, if indicated ● Provide available test results
Laboratory	Urine	
 ○ Pregnancy test ○ Urine dipstick/urinalysis, if indicated
	Blood	
 ○ HIV
	Genital	
 ○ PSA test ○ Gram stain for Nugent score, pH ○ CVF for PK and PD ○ CVL for soluble markers ○ Vaginal microbiota ○ TV, GC, CT testing, if indicated ○ Saline/KOH wet mount for candidiasis and/or BV, if indicated
	Anorectal	
 ○ RF for PK (if participant agrees)

Randomization Visit – Visit 3	
Component	Procedures
Study Product/Supplies	
 • Self-insertion of 1st dose • Dispense doses 2-3 for home insertion

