7.9 Clinical Evaluations and Procedures

Physical Examination and Medical History

The full physical examination will include general appearance, height, weight, vital signs, and evaluation of body systems as outlined in the MATRIX-001 SSP Manual. Participants will be asked about medications/therapies at every visit, including Visit 1. Vital signs and weight will be taken at all visits after Screening (after Visit 1). Study staff will ask about adverse events at all visits after baseline sampling (after visit 2). A full physical examination will be completed by the clinician at Screening. Thereafter, a directed physical examination will be performed to assess any complaints or symptoms as clinically indicated.

Pelvic Examination

Pelvic exams will be performed using visual inspection of external genitalia and using a speculum for examination of the cervix and vagina. Bimanual exam may be performed as needed (required at Screening Visit). Pelvic exams will be conducted at each visit for PK, PD and subclinical safety specimen collection and as indicated based on participant reports. CVF will be collected using swabs. Further specimen collection procedures will be detailed in the SSP. Biopsy areas will be checked for healing at applicable visits and as indicated.

Rectal Fluid Collection

For participants who consent to RF collection, this sample will be collected using a swab at certain visits to assess drug concentrations.

Cervicovaginal Tissue Collection

CVT will be obtained at Visits 2, 4 and 7 (per sampling timepoint randomization) to assess pharmacokinetics, pharmacodynamics, and anti-HIV activity.

The study site should carefully record the date and time of each collection of blood, CVF, and CVT biopsies. The time of sampling will be based on the time the first sample is taken (when multiple sample types are being collected at a time point, all samples should be collected within a short period). Samples collected outside the sampling windows below will be considered a protocol deviation:

- ± 4 hours outside of the 24 hour time point
- ± 8 hours outside of the 48 and 72 hour time points
- + 4 days outside of the 10 days time point

Note: Detailed information regarding the rectal and genital examination, as well as the associated procedures required for collecting specimens at each visit, can be found in the MATRIX-001 SSP Manual.

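### The NSAID and aspirin precaution around biopsies is stated differently in Protocol 6.7.2, 13.4.1 and Appendix III, leaving occasional NSAIDs and low-dose aspirin near a biopsy unclear

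*Protocol*

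**What the plan says.** Three places in the protocol deal with drugs that may increase bleeding when tissue is taken.

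- **13.4.1 Risks**, in the paragraph on biopsy collection: "Participants will be counselled to refrain from NSAIDs or aspirin use 3 days before and after PK sample collection".
- **6.7.2 Prohibited Practices** has two entries. For the period "72 hours before and after CVT biopsy collections" it lists one item: "Use of aspirin greater than 81 mg". For the whole study it bars "Use of any drugs which could prolong bleeding and/or clotting or otherwise interfere with study results per study criteria (i.e., daily NSAID use", followed by further examples and an open ending.
- **Appendix III**, which 6.7.1 makes the list of prohibited medications, names daily NSAIDs and, separately, anticoagulants and other drugs known to lengthen bleeding. It has no entry tied to biopsies.

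On when tissue is taken, Protocol 7.9 says "CVT will be obtained at Visits 2, 4 and 7 (per sampling timepoint randomization"). At Visit 2, participants "undergo baseline sample collection of CVF for PD, CVT for subclinical safety and PD, and cervicovaginal lavage (CVL) collection"; nothing is collected for PK. PK sampling starts at Visit 3, where participants "undergo baseline pre-insertion sample collection of CVL, CVF for PK, PD, and vaginal microbiota, and (if participant agrees) RF for PK", with no biopsy.

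**The concern.** This is one precaution with one purpose, limiting bleeding after a biopsy, yet the sections disagree on which drugs it covers, on whether aspirin has a dose threshold, and on what event starts the clock. Two sites could each follow the protocol in good faith and counsel women differently about a single NSAID tablet or a low-dose aspirin two days before a biopsy.

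Participant safety is the main stake. The protocol itself warns in 13.4.1 of bleeding after biopsy, of a small risk of heavier bleeding and, rarely, of a stitch. Uneven counselling across three sites comes next. There is also a limited link to the data: the primary endpoint is any treatment-emergent adverse event of Grade 2 or higher, with no exclusion for events caused by procedures, so a sufficiently severe bleed from a biopsy taken after dosing has begun could be counted.

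**Working it through.** No stated figure needs reproducing. The check compares the texts and then matches the visits.

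**1. The rules side by side**

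| Feature | 6.7.2, biopsy window | 6.7.2, whole study | Appendix III | 13.4.1 |
|---|---|---|---|---|
| NSAIDs | not listed | daily use given as the illustration | daily use | any use |
| Aspirin | above 81 mg | not named | not named | any dose |
| Other drugs that lengthen bleeding | not listed | barred in general terms | barred in general terms | not mentioned |
| Window | 72 hours each side | study duration | study duration | 3 days each side |
| Trigger | cervicovaginal biopsy | none | none | PK sample collection |

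The window length agrees, since 72 hours = 3 days. Drug, dose and trigger do not.

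**2. Test cases, two days before a Visit 4 or Visit 7 biopsy**

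- *A single NSAID dose.* Contrary to 13.4.1. Not in the 6.7.2 biopsy window. Under the general bans the answer depends on whether an occasional NSAID counts as a drug that lengthens bleeding, when the only NSAID wording given is daily use.
- *Aspirin at 81 mg or less.* Contrary to 13.4.1. Outside the 6.7.2 biopsy-window entry. If the general bans include aspirin, the 81 mg threshold in 6.7.2 has no function. If they do not, 6.7.2 and 13.4.1 disagree.
- *Aspirin above 81 mg.* Contrary to both 6.7.2 and 13.4.1.
- *Daily NSAIDs.* Contrary to all three places.

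The conflict is therefore confined to the first two cases.

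**3. Visits (Table 9 and Appendix I)**

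- Biopsy visits: {2, 4, 7}.
- Visits with any PK sample: {3, 4, 5, 6, 7, 8}.
- Visits with a biopsy for PK: {4, 7}.
- Biopsy visits outside 13.4.1, reading it as any PK sample: {2, 4, 7} minus {3, 4, 5, 6, 7, 8} = {2}.
- Biopsy visits outside 13.4.1, reading it as PK biopsies: {2, 4, 7} minus {4, 7} = {2}.
- Biopsy visits outside the 6.7.2 window: none.

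**4. Can a later PK window reach back to Visit 2?** The protocol says "Visit 3 should be scheduled 10-14 days after Visit 2, not less than 10 days after biopsy". Take Visit 2 as day 0, so a 3-day window around it runs from day −3 to day +3. The earliest window tied to Visit 3 opens on day 10 − 3 = +7. Visit 4 is 3 days after Visit 3, so on the PK-biopsy reading the earliest window opens on day 10 + 3 − 3 = +10. Neither reaches the Visit 2 biopsies.

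**5. Exposure (Table 9)**

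- Vaginal biopsies per woman: 1 (Visit 2) + 2 (Visit 4) + 3 (Visit 7) = 6.
- At EVMS, ectocervical biopsies add 2 + 2 + 1 to 2 = 5 to 6, giving 11 to 12 in all.
- At Visit 2: 1 of the 6 vaginal biopsies for every woman; at EVMS, 1 + 2 = 3 of the 11 to 12.

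These counts show how often the precaution is needed. They do not measure harm.

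**The case against.** The case for treating this as minor has real force.

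- **6.7.2 is the operative section.** Inclusion criterion 12 and the counselling section (7.8) both point to it, its window applies to every biopsy, and 13.4.1 is a risk narrative. This stands as far as coverage goes. A reader might infer that the Visit 2 biopsies are left without any precaution; the protocol does not support that, because 6.7.2 covers them. It does not settle what women are to be told, since 13.4.1 also describes counselling they will receive.
- **The general bans may fill the gap.** They do narrow it, and it would be wrong to say that 6.7.2 and Appendix III restrict nothing but daily NSAIDs. They do not close it: as shown above, reading aspirin into the bans empties the 81 mg threshold.
- **The PK wording in 13.4.1 probably means biopsies.** Its heading suggests so, and Protocol 7.2.2 uses PK tissue sampling in that sense. This stands. A literal reader might infer that drugs are restricted around Visits 3, 5, 6 and 8, where no tissue is taken, but that reading is strained and nothing here rests on it. The charitable reading still omits Visit 2.
- **The endpoint link is thin.** Also largely right. Bleeding from a Visit 2 biopsy starts before any dose, so it is neither treatment-emergent nor able to cause a product hold. By Visit 7 dosing is complete, so a bleed there cannot cause a hold either. Only a Visit 4 bleed could both count in the endpoint and lead to a hold.
- **A common procedures manual and standardised training may settle the matter.** They may; the manual is not at hand. Protocol 13.3, however, makes the protocol the directing document, so its own text should agree.

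**Conclusion.** The inconsistency is real and lies on the face of the protocol. Sections 6.7.2, 13.4.1 and Appendix III give different answers for occasional NSAIDs and for aspirin at or below 81 mg near a biopsy, and the 13.4.1 trigger misses one of three biopsy visits on either reading. It matters chiefly for participant safety and for uniform counselling at the three sites.

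A reader might go further and infer a biased or inflated primary safety result. The documents do not support that. Allocation is 1:1 within each site and the trial is double-blind, so a site's habits on NSAIDs or aspirin would fall on both arms; at most they would add noise or differences between sites. Bleeding after the Visit 4 and Visit 7 biopsies could count as a Grade 2 or higher event, but the protocol gives no rate of biopsy bleeding with or without these drugs, so no size can be derived. One woman is 1/30 = 3.3 percentage points of an arm, but that is the weight of any single event in a group of 30 and not an estimate of this effect.

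The conclusion rests on the protocol text alone. It does not judge which rule is clinically right.

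**What to change.** Reconcile 6.7.2, 13.4.1 and Appendix III. State the restriction once, giving the drugs covered (including whether NSAID use other than daily is included), any dose limit for aspirin, the window, whether biopsy collection or PK sampling is the trigger, and the visits by number. Make clear how the general ban on drugs that lengthen bleeding relates to any aspirin threshold. Have the other sections refer to that statement instead of restating it, and bring the counselling material and procedures manual into line. The sponsor's clinicians decide the content.

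The cost is wording in the protocol and counselling material. No procedure, visit, sample size or analysis changes.
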